9.0 Data and Specimen Long Term Storage and Use

9.1 *If you will store data or specimens for future use, describe where you will store the data or specimens, how long they will be stored, and how and by whom the data or specimens will be accessed:*

We will store data for the foreseeable future. Computer files will be kept on password-secured and managed Virginia Tech computer systems, while any paperwork will be kept locked in a restricted access office. The data access will be controlled by the PI, and access will be restricted to the research personnel.

9.2 *For specimens, list the data to be stored or associated with each specimen:*

N/A

9.3 *Describe the procedures to release data or specimens outside of the research team, including the process to request a release, approvals required for release, who can obtain data or specimens, and what data will be provided with specimens:*

Data will be made available to other researchers, with requests made via direct communication (email or phone). De-identified data files will be shared in response to other investigators direct request. Other researchers seeking access to the data associated with this research must seek their own separate IRB/HRPP approval/determination prior to accessing the data.

9.4 *Describe the identifiers to be included with stored data or specimens, as well as any key or code that could be used to make them identifiable. Describe where the code will be stored, who will have access to it, and when it will be destroyed:*

Identifiers will be a number ranging from 1 to the total number of participants enrolled. The key to make them identifiable will be kept in a separate computer file on a password-secured and managed Virginia Tech computer system. Only the study investigators will have access to the code. It will be destroyed 1 year after the completion of the project because at that time there will be no reason to need to contact study participants.

9.5 *Please select the identifiers you will obtain (whether directly from participants or from another source), including but not limited to:*

	Name
	Geographical subdivisions smaller than a state, including street address, city, county, precinct, zip code, and equivalent geocodes (note, the initial three digits of a zip code are not considered identifiable)
	Elements of dates (except year) for dates directly related to an individual, including birth date, admission date, discharge date, date of death, and single year of age over 89 and all elements of dates (including year) indicative of such age (note, such ages and elements may be aggregated into a single category of age 90+)
	Phone numbers
	Fax numbers
	Electronic mail addresses (e-mail)
	Social Security numbers
	Medical record numbers
	Health plan beneficiary numbers
	Account numbers
	Certificate/license numbers
	Vehicle identifiers and serial numbers, including license plate numbers
	Device identifiers and serial numbers
	Web Universal Resource Locators (URLs)
	Internet protocol (IP) address numbers
	Biometric identifiers, including finger and voice prints (audio recording)
	Full face photographic images and any comparable images (including video recording)
	Student record number or identification number
	User name for online or computer accounts

	Any other unique identifying number, characteristic, or code (note this does not mean the unique code assigned by the investigator to code the data): Age
-------------------------------------	--

10.0 Sharing of Results with Subjects

10.1 Describe whether you will share results (study results or individual subject results, such as results of investigational diagnostic tests, genetic tests, or incidental findings) with subjects or others (e.g., the subject's primary care physician). If so, describe how you will share the results and include this information as part of the consent document. Upload materials you will use to explain the results to subjects:

Results will not be shared with participants.

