7.0 Study Intervention(s)/Investigational Agent(s)

7.1 Describe the study interventions (including behavioral interventions) and/or investigational agents (e.g., drugs or devices) to be used in this study. Consider each of the items listed below:

- *Drug/Device Handling: If the research involves drugs or devices, describe your plans to store, handle, and administer the drugs or devices so that they will be used only on subjects, and only by authorized investigators.*
- *Describe whether any of the following will be used: microwaves, X-rays, DEXA scans, general anesthesia, or sedation*
- *If control of the drugs or devices used in this protocol will be accomplished by following an established, approved organizational SOP (e.g., Research Pharmacy SOP for the Control of Investigational Drugs, etc.), please reference the SOP in this section.*

Study Investigational Agents

The wearable sensors will be commercially-available inertial measurement units (<https://apdm.com/wearable-sensors/>) are the size of a matchbox and are specifically designed for wearing to measure body movements. They come with specialized straps to secure them on the body where desired. Three sensors will be worn by each participant including one on the top of each shoe using small pouches that are secured to the shoes using the shoe laces, and one sensor on the sternum using a light-weight shoulder harness worn under clothes.

The portable voice recorder (Sansa Clip Zip MP3 player) is a commercially-available device.

These sensors are self-contained, do not require any wires for connectivity, and will be used in a manner consistent with their approved use.

The laboratory-based equipment used to measure responses to LOBs will be an optoelectronic motion capture system. This system includes 13 cameras and a CPU unit for data collection. Reflective markers (approximately 1 cm in diameter) are placed on the participant at selected anatomical locations to measure body movements and responses to LOBs.

No microwaves, X-rays, DEXA scans, general anesthesia, or sedation will be used as a part of the intervention. However, DEXA scans will be used as a part of screening participants.

Study Interventions

21-1072 Validation and application of wearable sensors for capturing responses to losses of balance

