12.0 Inclusion and Exclusion Criteria

12.1 Describe how you will screen individuals for eligibility. When will screening occur and what procedures will you use? Upload any screening scripts or surveys to Protocol Management:

Screening will involve four phases. Participants will only proceed to the next phase if they pass preceding phases. The below Inclusion/Exclusion criteria apply to both non-balance training participants and balance training participants.

Phase 1

Inclusion criteria will be screened over the phone by an investigator (YL):

21-1072 Validation and application of wearable sensors for capturing responses to losses of balance

1. How old are you? [must be 65-80 to be eligible]
2. Are you willing to wear 3 small watch-sized sensors daily for two or three weeks (one on each foot and one on the chest) [must be yes to be eligible]
3. Have you had a lower limb amputation? [must be no to be eligible]
4. Do you weigh over 250 pounds? [must be no to be eligible]
5. Administer the Telephone Interview for Cognitive Status [must score 25 or higher to be eligible]

Phase 2

If the prospective participant passes phase 1, then the investigator will administer a health questionnaire during the same phone conversation. A copy of this health questionnaire is included with this application. No responses on this questionnaire will automatically make a participant ineligible. Rather, all responses to this questionnaire will be reviewed holistically by the health care specialist. No personally-identifiable information will be collected with this questionnaire. While it is rare for an individual age 65-80 to become pregnant, we will still include a question within the health questionnaire to ascertain pregnancy status.

Phase 3

The results of each health questionnaire will be reviewed by a health care specialist certified for clinical treatment of the geriatric population. No personally-identifiable information will be collected with this questionnaire. The health care specialist will then either:

- 1) accept the prospective subject for the next step of screening (see below);
- 2) decline the prospective subject for participation;
- 3) telephone the prospective subject for further evaluation and subsequent adjudication. If this occurs, personally-identifiable information may be collected directly by the interviewer.

Phase 4

Osteoporosis Screening

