14.3 If applicable, indicate the number of potential subjects you expect to screen for enrollment, and the number of subjects you will need to complete the research procedures:

N/A

14.4 If the study has more than one procedure, indicate the total number of subjects to undergo each procedure separately:

30 participants will be assigned to be non-balance training participants

30 participants will be assigned to be balance training participants, with 10 completing each of the three types of training under investigation (TT, NT, ST).

Other than these differences in balance training, all other testing will be the same for all participants.

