17.0 Risks to Subjects

17.1 List the reasonably foreseeable risks, discomforts, hazards, or inconveniences to the subjects related to the subjects' participation in the research. Include for the IRB's consideration a description of the probability, magnitude, duration, and reversibility of the risks. Consider physical, psychological, social, legal, privacy, and economic risks. Do not indicate "No risk" or "N/A." Instead, for studies with very low risk (e.g., anonymous online questionnaire on a mundane topic) indicate "The investigators are not aware of any risks from participation in this study." or "No more than risks than are found in everyday life." The example consent form presents a tabular method for risk information, which you can also use here. Common risk types include:

- *Physical (e.g., potential for pain, discomfort, infection)*
- *Psychological (e.g., potential for stress, discomfort, and/or embarrassment)*
- *Social (e.g., potential for discrimination or stigmatization and disruption of personal and family relationships)*
- *Legal (e.g., potential for disclosure of illegal activity, negligence)*
- *Privacy (e.g., potential for personal information being accessed, used, or disclosed without the subjects' knowledge or consent, breach of confidentiality/security)*
- *Economic (e.g., potential for individuals to lose access to economic services, employment, insurability)*

21-1072 Validation and application of wearable sensors for capturing responses to losses of balance

There are potential risks for participants in the proposed work.

1. During a DEXA scan, participants will be exposed radiation. The amount of radiation is less than 2 days' exposure to natural background radiation (NBR). By comparison, a chest X-ray uses the equivalent of about 3 days' exposure to NBR, and a flight from UK to USA is equivalent to approximately a week's exposure to NBR (<https://www.nhs.uk/conditions/dexa-scan/#:~:text=The%20amount%20of%20radiation%20used,a%20week's%20exposure%20to%20NBR>).
2. During balance training or testing, there is a risk of muscle strains, joint strains, other soft tissue injury, or broken bones. The risk of these outcomes is considered low given our safety measures described in 17.2.
3. During balance training or testing, there is a risk of participants overexerting themselves. This risk is considered low given our safety measures described in 17.2.

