18.0 Potential Benefits to Subjects

18.1 Describe the potential benefits that individual subjects might experience from participating in the research. Include the probability, magnitude, and duration of the potential benefits, as this will be useful to the IRB's risk:benefit analysis. Do not include benefits to society or others. Do not list monetary or non-monetary compensation for participation, as this is not a benefit. These should be included in section 2 or 3 of this document:

Participants who receive a DEXA scan will benefit from receiving this test at no cost. It can detect osteoporosis.

Balance training participants may benefit from balance training by improving their balance. However, this has not been formally evaluated at this time.

18.2 If applicable, specify that there are no anticipated direct benefits for participants:

N/A

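### Section 10.1 bars sharing results without exception, so nothing in the visible protocol gives a person excluded by the study DEXA scan their T-score or advice to see a physician

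*Combined protocol and SAP*

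**What the plan says.** The prompt in section 10.1 asks about study results and also about "individual subject results, such as results of investigational diagnostic tests, genetic tests, or incidental findings". It mentions the subject's primary care physician as a possible recipient. The whole answer is "Results will not be shared with participants".

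Section 18.1, on benefits to individual subjects, says: "Participants who receive a DEXA scan will benefit from receiving this test at no cost. It can detect osteoporosis".

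The scan serves as an eligibility screen. Section 7.1 notes that "DEXA scans will be used as a part of screening participants", and section 12.1 makes it Phase 4, with t < -2.5 as the exclusion threshold. A scan from the past year may be used instead. Section 19.3 has the study scan labelled by subject number, printed on paper, given to the investigator and kept out of email. Section 8.2 describes what follows a pass and is silent on what follows a fail.

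**The concern.** Detecting osteoporosis helps a person only if that person learns of it. As written, 10.1 tells staff to keep back the finding that 18.1 offers as a reason the scan is worth having. The person exposed to this is someone scanned only for the study whose score falls in the range that the protocol itself calls clinical osteoporosis. The investigator would hold that result on paper, and nothing visible directs anyone to pass it on or to suggest medical follow-up. This is a matter of participant welfare and of consistency between two sections that the IRB reads together. It is not a statistical matter.

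**Working it through.** No arithmetic is needed to test the inconsistency. The check was to follow the DEXA result through the protocol and look for any step that returns it to the person scanned.

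1. **The rule.** The 10.1 answer is unqualified, and its prompt expressly includes individual and diagnostic results. Nothing in the answer limits it to research findings.
2. **The benefit.** What 18.1 names is the free test, followed by the remark about detection. It promises no T-score, report or referral.
3. **Where the result goes.** Under 19.3 it goes to the investigator, on paper. No onward step is described.
4. **Other contacts that might close the gap:**
   - The specialist's telephone call in 12.1 Phase 3 comes before the scan and concerns the health questionnaire.
   - The debriefing in 8.6 follows the laboratory slip and trip session, which a person excluded at Phase 4 never reaches.
   - Physicians appear in 19.2 and 20.3 only as the source of an earlier scan.
5. **Who is affected.** Three groups need to be kept apart.
   - *Brought a scan from the past year:* they obtain the result from their own physician (19.2, 20.3). Not affected.
   - *Scanned for the study and enrolled:* section 12.1 says "Participants will only proceed to the next phase if they pass preceding phases", and all four phases must be passed. Enrolment therefore tells them that the scan did not exclude them. They lack only the number.
   - *Scanned for the study and excluded at Phase 4:* osteoporosis is the only Phase 4 criterion, so the reason can be inferred. They receive no T-score, no copy and no advice.
6. **How many.** Only the third group meets the harm described. Section 14.3 gives no screening number, and no section gives the share using an earlier scan or the expected share below the threshold. The lower bound is 0, and no upper bound can be derived.

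**The case against.** The strongest reply is that 10.1 was meant for research results, and that 18.1 takes for granted that the screening outcome becomes known. That is plausible, and wording elsewhere does not settle it. People being scanned are sometimes called participants, as in 17.1 ("During a DEXA scan, participants will be exposed radiation"), but also subjects and prospective participants. Even so, the 10.1 prompt asks about individual diagnostic results and the answer makes no distinction, so a member of staff following it has no stated basis for handing over the scan.

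A second reply is that the consent form or telephone script may cover disclosure. Sections 24.1 and 25.2 require written consent before a study scan, so the form is a natural place for it. Neither document is visible, and absence from the protocol does not show absence from them. This stands, and it is the main reason the point is minor. If the form does promise the result, 10.1 would still need to agree with it.

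A third reply is that exclusion at Phase 4 already tells the person the outcome. That is largely true, but an inference supplies neither a figure to take to a physician nor a prompt to go.

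A reader might also infer something stronger: that up to 60 enrolled people, or the half without training ("30 participants will be assigned to be non-balance training participants"), are denied a promised benefit. The documents do not support that. Everyone enrolled passed Phase 4 and effectively knows the scan was not in the exclusion range, and 18.1 promises no numeric report.

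**Conclusion.** The point holds as a minor inconsistency with a participant-safety consequence. Read literally, 10.1 withholds an osteoporosis-range result from a person scanned for the study and excluded because of it, and no visible section provides otherwise. The number affected is unknown and may be small or zero. Enrolled participants lack only the T-score itself.

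The conclusion assumes that 10.1 is applied as written and that the unseen consent form and telephone script do not already provide for disclosure. If they do, only the wording of 10.1 needs to be reconciled. It would go too far to say that the study's risk-benefit balance fails: nothing visible makes its acceptability depend on the DEXA benefit, and 17.1 puts the radiation at less than two days of natural background exposure. No endpoint, hypothesis, analysis or sample size is affected.

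**What to change.** Check the consent form first. Then add one exception to the sentence in 10.1, for example: *except the DEXA screening result, which is given to each person scanned for the study, including anyone excluded for t < -2.5, with a copy of the printout and advice to discuss it with their own physician.* Align the consent form if it does not already say this. A paper copy respects the bar on email in 19.3.

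The cost is a short IRB amendment and a little staff time per scan. No study clinician is needed to interpret the result, because the person is directed to their own physician.

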11.0 Study Timelines

11.1 Describe:

- *The duration of an individual subject's participation in the study (for example, 1 hour, 2-4 weeks, 3-5 years).*
- *The amount of time expected to enroll all study subjects (weeks, months, years, etc.)*
- *The amount of time expected for the investigators to complete this study including primary data analyses.*

Duration of participant's participation: about 7 weeks

Time expected to enroll all study participants: 18 months

Amount of time expected for investigators to complete study: 24 months

12.0 Inclusion and Exclusion Criteria

12.1 Describe how you will screen individuals for eligibility. When will screening occur and what procedures will you use? Upload any screening scripts or surveys to Protocol Management:

Screening will involve four phases. Participants will only proceed to the next phase if they pass preceding phases. The below Inclusion/Exclusion criteria apply to both non-balance training participants and balance training participants.

Phase 1

Inclusion criteria will be screened over the phone by an investigator (YL):

21-1072 Validation and application of wearable sensors for capturing responses to losses of balance

1. How old are you? [must be 65-80 to be eligible]
2. Are you willing to wear 3 small watch-sized sensors daily for two or three weeks (one on each foot and one on the chest) [must be yes to be eligible]
3. Have you had a lower limb amputation? [must be no to be eligible]
4. Do you weigh over 250 pounds? [must be no to be eligible]
5. Administer the Telephone Interview for Cognitive Status [must score 25 or higher to be eligible]

Phase 2

If the prospective participant passes phase 1, then the investigator will administer a health questionnaire during the same phone conversation. A copy of this health questionnaire is included with this application. No responses on this questionnaire will automatically make a participant ineligible. Rather, all responses to this questionnaire will be reviewed holistically by the health care specialist. No personally-identifiable information will be collected with this questionnaire. While it is rare for an individual age 65-80 to become pregnant, we will still include a question within the health questionnaire to ascertain pregnancy status.

Phase 3

The results of each health questionnaire will be reviewed by a health care specialist certified for clinical treatment of the geriatric population. No personally-identifiable information will be collected with this questionnaire. The health care specialist will then either:

- 1) accept the prospective subject for the next step of screening (see below);
- 2) decline the prospective subject for participation;
- 3) telephone the prospective subject for further evaluation and subsequent adjudication. If this occurs, personally-identifiable information may be collected directly by the interviewer.

Phase 4

Osteoporosis Screening

The prospective participant must not have clinical osteoporosis as indicated by bone mineral density of the lumbar vertebra and proximal femur of $t < -2.5$ obtained from Dual Energy X-ray Absorptiometry (DEXA). This assessment will be based upon a DEXA scan performed for this study, or DEXA scan completed within the last year.

Participant must pass all four phases to be eligible to participate.

12.2 Describe the eligibility criteria that define who will be included and who will be excluded from enrollment for each procedure of your study.

Include any geographic criteria (e.g., Virginia Tech undergraduate students, a national sample of adults with engineering degrees, minors aged 8-12 in the New River Valley, university faculty in Virginia and Paris, France):

21-1072 Validation and application of wearable sensors for capturing responses to losses of balance

Phase 1 - Inclusion criteria screened over the phone:

1. How old are you? [must be 65-80 to be eligible]
2. Are you willing to use wear 3 small watch-sized sensors daily for two weeks (one on each foot and one on the chest) [must be yes to be eligible]
3. Have you had a lower limb amputation? [must be no to be eligible]
4. Do you weigh over 250 pounds? [must be no to be eligible]
5. Administer the Folstein Mini-Mental Status Exam [must score 25 or higher to be eligible]

Phase 2 - Health questionnaire (see attached to this application)

Phase 3 - Review of health questionnaire by health professional.

Phase 4 - Osteoporosis screening. The prospective participant must not have clinical osteoporosis as indicated by bone mineral density of the lumbar vertebra and proximal femur of $t < -2.5$ obtained from Dual Energy X-ray Absorptiometry (DEXA). This assessment will be based upon a DEXA scan to be scheduled for this study, or one they have had completed within the last year.

12.3 Indicate specifically whether you will include or exclude each of the following special populations: (You may not include members of these populations as subjects in your research unless you indicate them in the description of your subject population.)

- *Minors, as defined by state law where the study is performed (infants, children, teenagers)*
- *Pregnant women (can be included in minimal risk studies by mentioning in section 13.1)*
- *Prisoners (including all incarcerated individuals)*
- *Adults not capable to consent on their own behalf*

Minors will be excluded

Pregnant women will be excluded based upon self report.

Prisoners will be excluded

Adults not capable to consent on their own behalf will be excluded

